1 BACKGROUND

While exploring structure-activity relationships of organic ligands possessing an N⁴O² donor core [1-3], we identified a gallium-68-radiopharmaceutical (named herein as ⁶⁸Ga-Galmydar) that demonstrates high extraction into the myocardium of mice, rats, and rabbits while also displaying efficient clearance from the blood pool. Additionally, [⁶⁸Ga]Galmydar is recognized by MDR1 P-glycoprotein (Pgp) [4] and Breast Cancer Resistance Protein (BCRP, ABCG2) [5] as their efficient transport substrate, and thus it exploits transporter-mediated excretion pathways from the blood and liver, resulting in high heart/blood and heart/liver ratios 60-minute post injection. Live cell-imaging of rat cardiomyoblasts using Galmydar (fluorescent probe) shows its localization within the mitochondria following permeation within cells indicating excellent correlation with radiotracer uptake data [4,5]. [⁶⁸Ga]Galmydar micro positron emission tomography (PET)/computed tomography (CT) imaging of rat and rabbit hearts show high myocardial uptake and high target/background contrast. Following ligation of the left anterior descending (LAD) coronary artery in rat and rabbits, PET/CT imaging clearly showed the hypoperfused region of the left ventricle wall. These hypoperfused regions of the myocardium correlated well to the same ex vivo regions by histochemical staining post imaging. [⁶⁸Ga]Galmydar has also shown sensitivity in monitoring ischemia caused by transient ligation of LAD in rabbits on PET imaging, also with positive correlation of the ischemic region with ex vivo histology. Radiation dosimetry studies in mice extrapolated to human dosimetry estimates using Medical Internal Radiation Dosimetry (MIRD) methodology and employing FDA guidelines (21 CFR 312) of maximum allowable dose to any organ of 50 mSV indicate an allowable maximum injection dose of 8 mCi in humans. This is comparable to ¹⁸F-Flurpiridaz, another myocardial perfusion imaging (MPI) agent undergoing Phase 3 studies. Importantly, [⁶⁸Ga]Galmydar does not demonstrate any remarkable clinical pathology (toxicology) in critical organs following intravenous administration of a single dose (1000 fold excess of an IV imaging dose) of an unlabeled agent into rats over 14 days. Finally, compared to ¹³N-ammonia (a positive control), [⁶⁸Ga]Galmydar also demonstrates similar radiotracer characteristics and, in particular, comparable myocardial first pass extraction of about 70-90% so that regadenosone-induced stress myocardial perfusion and myocardial blood flow (MBF) quantification employing kinetic modeling should be comparable [6,7,8]

Thus, this study is designed to demonstrate feasibility of [⁶⁸Ga]Galmydar for the noninvasive detection and characterization of subclinical and clinically-manifest coronary artery disease (CAD) in conjunction with PET by its comparative analysis to ¹³N-ammonia PET rest and stress studies in human subjects (n=20, 10 males and 10 females). Secondary aims are to evaluate dosimetry, biodistribution, and safety, and imaging characteristics following a single injection in normal healthy volunteers at rest (n=8, 4 males; 4 females).

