1.2 Study Rationale

1.2.1 Dosimetry Group

The successful implementation of [⁶⁸Ga]Galmydar in humans could provide a new mechanism-driven tracer for PET MPI, and successful realization of aims could ultimately take PET MPI to underserved regions nationwide and developing countries worldwide, where an ¹⁸F-distribution business model would have limitations. [⁶⁸Ga]Galmydar PET MPI could enable quantification of myocardial flow reserve (MFR= stress MBF / rest MBF that carries important diagnostic and prognostic information) that may play an additional important role to evaluate or monitor the effectiveness of preventive medical care or the treatment response on the function of the heart vessels in CAD individuals. These benefits combined with the minimal risks weight the ratio in favor of moving the PET radiotracer [⁶⁸Ga]Galmydar into human subjects. This component of the study will determine the biodistribution and calculate the radiation dosimetry of [⁶⁸Ga]Galmydar in normal healthy volunteers. Our radiation dosimetry studies in mice [9] extrapolated to human dosimetry estimates using MIRD methodology suggest an allowable maximum injection dose of 8 mCi in humans. The maximum Effective Dose for one 8 mCi intravenous administration of [⁶⁸Ga]Galmydar and three whole-body CT scans with CT attenuation scans results in a gender average radiation dose of 2.84 rem that is well within 57% of the allowable annual dose for radiation workers.

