5.3 Drug Administration

The Sponsor-Investigator will adhere to the procedures and requirements in accordance with applicable policies of the Radiation Safety Committee (RSC) at Washington University and the U.S. Nuclear Regulatory Commission (NRC).

A PET-certified medical professional will draw, administer, and assay the dosage in a dose calibrator before and after the administration of all radiotracers.

The Dosimetry group will receive one single intravenous administration of $8 \text{ mCi} \pm 20\%$ (6.4–9.6 mCi) of ⁶⁸Ga-Galmydar. The Rest/Stress Group will receive two intravenous administrations of ⁶⁸Ga-Galmydar, $4 \text{ mCi} \pm 20\%$ (3.2–4.8 mCi) during rest and $6 \text{ mCi} \pm 20\%$ (4.8–7.2 mCi) during the stress of [⁶⁸Ga]Galmydar on the PET MPI Imaging Day-1. The acceptable mass for each [⁶⁸Ga]Galmydar administration is $\leq 10 \text{ } \mu\text{g}$. On Imaging Day-2, subjects will receive two single intravenous administrations each of $10 \text{ mCi} \pm 20\%$ (8–12 mCi) of N-13 Ammonia.

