6.3 Dosimetry Group - PET/CT Imaging

Healthy adult normal volunteers enrolled in the dosimetry group will come to the Center for Clinical Imaging Research (CCIR) facility, a Washington University facility, located on the 10th floor of Barnes-Jewish Hospital for screening and PET imaging.

The following assessments and procedures will be performed:

- VS, 12-lead ECG, safety labs, and a brief physical exam pre and post injection and prior to discharge from the CCIR to home or transfer to the CTRU as described above;
- All required safety assessments prior to the administration of [⁶⁸Ga]Galmydar and monitor ECG rhythm and HR as described above. Monitor ECG-rhythm and HR during imaging;
- Administer an intravenous bolus injection of 8 mCi ± 20% (6.4–9.6 mCi) with a mass of ≤ 10 µg of [⁶⁸Ga]Galmydar followed by a 10 mL normal saline flush;
- Whole-body PET image acquisition from head to mid-thigh. Imaging of subjects will be at three time points spanning from immediately after injection up to 4-hours after

[⁶⁸Ga]Galmydar injection. A low-dose spiral CT scan (120 kVp, 50 mAs) will be obtained for attenuation correction. Begin whole-body PET image acquisition from the head to mid-thigh immediately post [⁶⁸Ga]Galmydar injection for 60-min and repeat at 2 hours and 4 hours.

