11.3.1 Low-dose CT

The effective dose (ED) for one whole-body CT protocol conducted at a single time point is 0.49 rem (50 mAs). A one-bed position low dose CT (50 mAs) over the heart for attenuation correction (CT-AC) is 0.18 rem.

11.3.2 [⁶⁸Ga]Galmydar and ¹³N-Ammonia PET

The effective dose for [⁶⁸Ga]Galmydar is 0.103 rem/mCi (gender averaged). The effective dose for ¹³N-ammonia is 0.007 rem/mCi.

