11.3.2.1 Dosimetry Group

A single dosage of 8 mCi \pm 20% (6.4–9.6 mCi) with a mass of \leq 10 μ g is planned for [⁶⁸Ga]Galmydar administration for the Dosimetry group. The effective dose for a whole-body PET/CT imaging protocol includes a single intravenous administration of 8 mCi of [⁶⁸Ga]Galmydar, three whole-body CT scans and four CT-AC scans is 2.81 rem and 2.87 rem for male and females.

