- f) Vital signs will be obtained at screening, baseline within 5 to 15-min pre-injection and within 5 to 15-min post injection, end of first imaging session, beginning of each delayed imaging session, and prior to discharge from the imaging facility. Repeat as needed.
- g) A 12-lead ECG will be performed at screening, baseline within 60-min prior to injection, within 5 to 15-min post-injection, end of first imaging session, and prior to discharge from imaging facility. Repeat as needed.
- h) Monitoring during the PET study: Place a blood pressure cuff on the opposite arm used for the radiotracer administration to measure blood pressure and heart rate. Place electrodes on the participant's chest for continuous ECG monitoring and electrodes to obtain 12-lead ECG.
- i) Obtain a low-dose CT-AC (50 mAs) prior to the 8 mCi \pm 20% (6.4–9.6 mCi) IV injection of [⁶⁸Ga]Galmydar followed by a 10 mL saline flush. Begin whole-body PET image acquisition from the head to mid-thigh immediately post [⁶⁸Ga]Galmydar injection for 30-min and repeat at 2 hours and 4 hours.
- j) Phone follow-up will occur within 2-3 days and repeated at 5-7 days or as late as 14-days post [⁶⁸Ga]Galmydar injection. If any of the days are not business days, the follow-up phone call may occur the following business day.

Table 3. Schedule of Activities—Rest/Stress Group

| Procedure | Pre-Screen ^(a) | Screening Visit ^(b) | IMAGING DAY-1 [⁶⁸ Ga]Galmydar PET/CT ^(k) | | | IMAGING DAY-2 ¹³ N-Ammonia PET/CT ^(l) | | | Phone Follow-up ^(o) |
|--|---------------------------|--------------------------------|--|--------|--------------------------|--|--------|--------------------------|--------------------------------|
| | | | Rest | Stress | Discharge ^(m) | Rest | Stress | Discharge ^(m) | |
| Written Informed Consent | | X | | | | | | | |
| Inclusion/Exclusion Criteria | X | X | | | | | | | |
| Adverse Events ^(b) | | X | X | X | X | X | X | X | X |
| Medical Records (EHR) ^(c) | X | X | X | X | X | X | X | X | X |
| Demographics | X | X | | | X | | | | |
| Medical History ^(a,d) | X | X | | | | | | | |
| Concomitant Medication ^(b) | X | X | X | X | | X | X | | X |
| Physical Exam/Evaluation ^(d) | | X | | | | | | X | |
| Body Weight and Height ^(b) | | X | | | X | | | | |
| IV placement ^(e) | | | X | | | X | | | |
| Clinical safety labs ^(f) | | | X | X | X | | | | X |
| Vital Signs ^(g) | | | X | X | X | X | X | X | |
| 12-lead Electrocardiogram ^(h,i) | | | X | X | | X | X | | X |

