- j) PET/CT imaging: Obtain a low-dose CT-AC (50 mAs) prior to each rest and stress radiotracer injection. If the same IV line is used for both the regadenoson and radiotracer injections, wait 10-20 sec after the normal saline flush post regadenoson injection before injecting the radiotracer.

k) [⁶⁸Ga]Galmydar Imaging Day-1:

- *Rest PET*: Administer 4 mCi ±20% (3.2–4.8 mCi) of [⁶⁸Ga]Galmydar IV injection followed by a 10 mL saline flush and immediately begin up to a 30-min list-mode data acquisition for a single bed position at the level of the heart. The interval between the rest and stress [⁶⁸Ga]Galmydar PET acquisitions *should be no less than 2 hours and no greater than 4 hours*.
- *Stress PET MPI*: Administer a rapid (10-sec) regadenoson IV injection (0.4 mg/5 mL), followed by 5 mL saline flush; 30-sec post regadenoson injection, administer 8 mCi ±20% (6.4–9.6 mCi) of [⁶⁸Ga]Galmydar IV injection followed by a 10 mL saline flush. Begin up to a 30-min list-mode data acquisition for a single bed position at the level of the heart.

l) ¹³N-Ammonia Imaging Day-2:

- *Rest PET*: Administer an IV bolus injection of 10 mCi ±20% (8–12 mCi) of ¹³N-Ammonia followed by a 10 mL saline flush and immediately begin a 10-min list-mode data acquisition (if the anterior-posterior diameter of the chest is >50cm increase to 15-min) for a single bed position at the level of the heart. The interval between the rest and stress ¹³N-ammonia acquisitions should be *no less than 1-hour*.
- *Stress PET MPI*: Administer a rapid (10-sec) regadenoson IV injection (0.4 mg/5 mL), followed by 5 mL saline flush; 30-sec post regadenoson injection, administer 10 mCi ±20% (8–12 mCi) of ¹³N-Ammonia IV bolus injection followed by a 10 mL saline flush. Begin a 10-min list-mode data acquisition (if the anterior-posterior diameter of the chest is >50cm increase to 15-min) for a single bed position at the level of the heart.

m) Transfer [⁶⁸Ga]Galmydar participants to CTRU for post imaging safety assessments and discharge.

Discharge ¹³N-Ammonia participants from the CCIR.

n) Contact [⁶⁸Ga]Galmydar participants by phone within 2-3 days post [⁶⁸Ga]Galmydar injection.

[⁶⁸Ga]Galmydar and ¹³N-ammonia imaging visits will be separated by a minimum of 3-days and not before the follow-up phone call is complete for capturing participant adverse events following the administration of [⁶⁸Ga]Galmydar. If any of the days are not business days, the phone call may occur the following business day.

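### The dosimetry dose range and Table 3's stress dose both extend above the protocol's own 8 mCi maximum, and the dosimetry-group effective dose does not match the scans listed for it

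*Combined protocol and SAP*

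**What the plan says.** **The ceiling.** Section 1 (Background) applies a 50 mSv limit to any organ and concludes that the extrapolated mouse data "indicate an allowable maximum injection dose of 8 mCi in humans". Section 1.2.1 repeats that these estimates "suggest an allowable maximum injection dose of 8 mCi in humans".

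**Dosimetry-group dosing.** Section 6.3 instructs: "Administer an intravenous bolus injection of 8 mCi ± 20% (6.4–9.6 mCi". Sections 5.3 and 11.3.2.1 give the same range, as does Table 2 note i: "6.4–9.6 mCi) IV injection of [⁶⁸Ga]Galmydar followed by a 10 mL saline flush".

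**Stress dosing.** Section 5.3 sets the stress injection at 6 mCi ±20%, "4.8–7.2 mCi) during the stress of [⁶⁸Ga]Galmydar on the PET MPI Imaging Day-1". Section 6.4.1.2 gives the same range and describes 6 mCi as a maximum; section 11.3.2.2 computes its dose totals at 6 mCi. Table 3 note k tells staff to "administer 8 mCi ±20% (6.4–9.6 mCi) of [⁶⁸Ga]Galmydar IV injection followed by a 10 mL saline flush".

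**Effective dose.** Section 11.3.2.1 covers one 8 mCi injection with "three whole-body CT scans and four CT-AC scans is 2.81 rem and 2.87 rem for male and females". Section 1.2.1 quotes the average, 2.84 rem, as 57% of the annual allowance for radiation workers. The unit doses are in section 11.3: 0.103 rem per mCi of tracer, 0.49 rem per whole-body CT, and for a one-bed low-dose CT "over the heart for attenuation correction (CT-AC) is 0.18 rem".

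**The concern.** There are three separate conflicts in the radiation-safety text.

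1. A nominal dose set at the stated maximum, with a symmetric tolerance, puts the upper half of the permitted window above that maximum. Section 5.3.1 asks for authorized-user approval only outside the allowable range, so nothing is triggered between 8 and 9.6 mCi. Section 10.7 requires prompt notice of excessive radiation exposure, but with both 8 and 9.6 mCi in the text it is unclear whether 9.6 mCi would count.
2. Staff working from Table 3 would inject a different stress activity from staff working from section 6.4.1.2. Under section 5.3 every rest/stress injection stays below 8 mCi; under Table 3 it need not. Up to 30 subjects are affected.
3. The dosimetry-group effective dose does not correspond to the scans it is said to include.

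The tracer has no prior human data, the ceiling comes from mice, and the dosimetry subjects are healthy volunteers. The activity ceiling and the effective dose are the figures the oversight committees rely on.

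**Working it through.** **Inputs** (sections 1, 5.3, 11.3.1 and 11.3.2): maximum 8 mCi; organ limit 50 mSv; permitted upper activity 9.6 mCi; 0.103 rem/mCi for the study tracer; 0.007 rem/mCi for ¹³N-ammonia; 0.49 rem per whole-body CT; 0.18 rem per CT-AC.

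**Do the unit doses reproduce the protocol's other totals?**
- Rest/stress tracer day, 4 + 6 mCi and two CT-AC: 10 × 0.103 + 2 × 0.18 = 1.39 rem (stated 1.40).
- Ammonia day, 20 mCi and two CT-AC: 20 × 0.007 + 2 × 0.18 = 0.50 rem (stated 0.51).

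Both agree within 0.01 rem, so the unit doses are the ones in use. Working back from the stated totals, one CT-AC is (1.40 − 0.62 − 0.41)/2 = 0.185 and (0.51 − 0.14)/2 = 0.185 rem.

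**Dosimetry-group total.** Stated average: (2.81 + 2.87)/2 = 2.84 rem. The formula is 8 × 0.103 + 3 × 0.49 + n × 0.18, where n is the number of CT-AC scans. The range lets each unit dose vary by half its last digit.

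| CT-AC scans | Sum (rem) | Rounding range (rem) | Sum minus 2.84 |
|---|---|---|---|
| 3 | 0.824 + 1.47 + 0.54 = 2.834 | 2.800–2.868 | −0.006 |
| 4 (as listed) | 0.824 + 1.47 + 0.72 = 3.014 | 2.975–3.053 | +0.174 |

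The stated average implies (2.84 − 0.824 − 1.47)/0.18 = 3.03 scans. With four scans, even the lowest value that rounding allows (2.975) is above the higher, female figure (2.87). The gap is about one CT-AC. Against the 5 rem that the stated 57% implies, 2.84/5 = 57% and 3.014/5 = 60%.

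**Dosimetry activity against the ceiling.** 9.6/8 = 1.20. The documents give no organ dose per mCi, so let L be the activity that delivers 50 mSv to the limiting organ. The organ dose at 9.6 mCi is then 50 × 9.6/L:
- L = 8 exactly: 60 mSv.
- L between 7.5 and 8.5 (8 as a rounded figure): 64.0 down to 56.5 mSv.
- L = 8.99 (rounded down to 8): 53.4 mSv.
- Break-even: L = 9.6.

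Effective dose at 9.6 mCi: 9.6 × 0.103 = 0.989 rem from the tracer, so 0.989 + 1.47 + 0.54 = 3.00 rem with three CT-AC scans and 3.18 rem with four.

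**Stress injection.**

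| | Sections 5.3, 6.4.1.2 | Table 3 note k |
|---|---|---|
| Nominal stress activity | 6 mCi | 8 mCi (8/6 = 1.33) |
| Upper limit, one injection | 7.2 mCi | 9.6 mCi |
| Upper limit, rest + stress | 4.8 + 7.2 = 12.0 mCi | 4.8 + 9.6 = 14.4 mCi |
| Effective dose at nominal activity, two CT-AC | 1.39 rem (stated 1.40) | 12 × 0.103 + 0.36 = 1.60 rem |

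**The case against.** **The ±20% is an ordinary dispensing tolerance.** It is applied to every tracer in section 5.3, including ¹³N-ammonia, and the 8 mCi figure is only an extrapolated estimate. That would answer the point if 8 mCi were just a target. The protocol calls it the allowable maximum in two places, and a tolerance cannot run above a maximum without being justified.

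**A breach of the organ limit is not demonstrated.** This stands. If 8 mCi was chosen conservatively from a true limit of 9.6 mCi or more, 50 mSv is not exceeded, and the supporting organ-dose table may be in the IND. But the protocol would then be wrong to call 8 mCi the maximum, so the two statements need reconciling either way.

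**There are safeguards.** FDA, IRB and RDRC approvals precede the study, and section 12 requires review of biodistribution and safety in the first two volunteers before the others are imaged. Neither caps activity, and the first two could themselves receive 9.6 mCi.

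**Table 3 is a lone outlier in a summary table.** This is fair: section 6 describes the schedules as summaries, and all the other dosing text says 6 mCi. It suggests which figure is probably left over, but the note is in the current schedule that section 6 directs readers to.

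**The effective-dose mismatch is small and clerical.** It is: 0.17 rem, with either total well below 5 rem. Section 11.3 mentions an extra CT-AC for rescheduled or interrupted scans, which may explain how three became four, but it does not repair the sum.

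**Conclusion.** All three conflicts are in the current text and must be corrected. The first two carry the weight.

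- **Ceiling:** the dosimetry range permits 9.6 mCi in one injection, 20% above the protocol's own maximum. The consequence for organ dose is conditional: about 60 mSv if 8 mCi equals 50 mSv, 53 to 64 mSv over the rounding cases shown, and no excess only if the true limit is 9.6 mCi or higher.
- **Stress dose:** Table 3 is 33% above the body text at nominal activity and allows the same 9.6 mCi. It would raise the tracer-day effective dose from the stated 1.40 rem to about 1.60 rem.
- **Dosimetry total:** the listed contents sum to 3.01 rem (2.98–3.05), not 2.84. Three CT-AC scans fit the stated total; four do not. Only the average of the sexes can be checked, because sex-specific coefficients are not given.

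The documents do not settle which activity, limit or scan count was intended.

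**What to change.** 1. **Dosimetry activity.** Cap it at 8 mCi in sections 5.3, 6.3, 11.3.2.1 and Table 2 note i (for example 6.4–8 mCi). Otherwise restate the ceiling in sections 1 and 1.2.1 and show the limiting-organ dose at 9.6 mCi.
2. **Stress activity.** Change Table 3 note k to 6 mCi ±20% (4.8–7.2). If 8 mCi is really intended, sections 5.3, 6.4.1.2 and 11.3.2.2 must change instead, with the tracer-day total near 1.60 rem, and the ceiling problem then extends to this group.
3. **Effective dose.** In section 11.3.2.1, either correct the CT-AC count to three or correct the average total to about 3.01 rem with matching male and female figures. In the second case also update section 1.2.1 to about 60%.

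The cost is wording in sections 1, 1.2.1, 5.3, 6.3, 11.3.2.1 and Tables 2 and 3. Capping at 8 mCi narrows the usable activity window for eight volunteers. No endpoint, sample size or analysis is affected.

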1.1 Significance

Existing state-of-the art MPI tracers have certain limitations, such as low sensitivity, poor spatial resolution, attenuation artifacts, slow liver clearance, and nonlinearity of MBF at high flow rates.

To overcome these shortcomings, new MPI agents are desired. Utility of PET MPI agents, such as ¹³N-ammonia, and H₂¹⁵O is limited due to the requirement for proximity to a multimillion dollar cyclotron. In addition, myocardial perfusion examinations using ⁸²RbCl₃ suffer from low first pass extraction, low spatial resolution because of the higher positron range, and short radionuclide half-life due to both potential oversaturation of the detectors at the beginning of the acquisition due to injected high dose, and low count statics and suboptimal signal/noise ratios at later time points. Conversely, Gallium-68 based agents offer tremendous advantages as potential PET MPI agents and are likely to widely resolve these shortcomings.

Using Gallium-68, Galmydar incorporates four important components into its pharmacophore design: a) a rationale built upon exploiting transporter-mediated efflux pathways (Pgp and BCRP substrates) to facilitate excretion from neighboring tissues, such as liver and blood, to allow high heart-to-liver and heart-to-blood ratios enabling high target/ background ratios, b) moderately hydrophobic cationic probes possessing a delocalized positive charge on their molecular surface to allow penetration of myocardium in response to favorable negative plasma- and mitochondrial transmembrane potentials, thereby producing high first-pass extraction and minimal washout from myocardium during imaging sessions, c) a PET agent that incorporates a generator-produced radionuclide, ⁶⁸Ga (t_{1/2} = 68 min), to allow production of the radiopharmaceutical independent of the availability of a nearby cyclotron, and d) a potential technology conducive for business models of kit distributions comprising a ligand with a long shelf-life, thereby enabling onsite production for imaging in clinics. These combined elements indicate that further development of [⁶⁸Ga]Galmydar and its translation is based upon the strong scientific premise.

Also, using both rats and rabbits, micro-PET and nano-single photon emission computed tomography (SPECT) imaging directly showed high heart uptake of [⁶⁷Ga]Galmydar and rapid clearance from the liver within 30 min post injection, indicating its ability to serve as a potential myocardial perfusion agent for both PET and SPECT. In this regard, the faster kinetics and short half-life of [⁶⁸Ga]Galmydar may lead to improved dosimetry over ¹⁸F-Flurpiridaz, another mitochondrial complex I targeted MPI agent. Moreover, Complex I deficiency, which is clinically and genetically heterogeneous, can present with hypertrophic cardiomyopathy that could either be isolated or associated with other comorbidities. . Therefore, the lower uptake of a given mitochondrial Complex I targeted agent, such as ¹⁸F-Flurpiridaz could also potentially be influenced by these complications. Compared with the performance of ¹⁸F-Flurpiridaz in these areas, the design of [⁶⁸Ga]Galmydar is based upon an established and successful biochemical model for development of MPI agents. Importantly, the robust biochemical validation of Galmydar in *cellulo* (radiotracer, and optical imaging assays) and in mice, rat, and rabbit models of both permanent and transient LAD ischemia, with response to pharmacological stress, toxicology studies in rats, and dosimetry studies *in vivo*, provide us with a sound platform for further versatile molecular imaging probes for quantifying myocardial perfusion and MBF in humans.

